8.1.4.4 Guidelines for monitoring and management of significant changes in renal function

If at any time after Randomization (Visit 2 [Day 1]) a participant experiences ANY of the following, the participant will undergo a repeat confirmatory assessment as soon as is reasonably possible, preferably within 3 to 7 days of the laboratory result becoming available:

- A >25% decrease in eGFR from baseline, calculated using the Chronic Kidney Disease Epidemiology Collaboration equation;
- An eGFR <15 mL/min/1.73 m², calculated using the Chronic Kidney Disease Epidemiology Collaboration equation; and/or
- An increase in serum creatinine of ≥ 0.3 mg/dL (≥ 26.5 µmol/L) from baseline.

In consultation with the Medical Monitor and/or nephrologist, if no alternative etiology is determined, the study drug should be discontinued if participants experience an unexplained, confirmed increase in serum creatinine of ≥ 0.3 mg/dL (≥ 26.5 µmol/L) from baseline or an unexplained, confirmed $\geq 25\%$ decrease in eGFR from baseline.

If any of these individual laboratory parameters are confirmed, such events of decline in renal function should be recorded as an ESI.

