- b. A participant who is screened and does not meet the study eligibility criteria may be considered for rescreening upon Sponsor and/or Medical Monitor consultation and approval. Rescreened participants will be assigned a new participant number. Rescreening should occur no less than 5 days after the last screening visit.
- c. Participants who discontinue study drug between Visit 2 (Day 1) and Visit 3 (Day 28) or at Visit 3 (Day 28) should complete an EOT Visit at Day 28, return to complete Visit 4 (Day 84), and return to complete the Safety Follow-up Visit (Day 112). In addition, participants who withdraw from the study should complete an EOT Visit. Participants who discontinue study drug between Visit 3 (Day 28) and Visit 4 (Day 84) will not undergo an EOT Visit but continue with study visits per protocol.
- d. Participants will be required to sign an ICF before any study-related procedures are performed.
- e. Confirm the participant continues to meet the inclusion and exclusion criteria and assess any updates since Screening (Visit 1).
- f. Weight and height will be measured at Screening (Visit 1) and will be used to calculate body mass index. Measurement of weight should be performed with the participant dressed in indoor clothing, with shoes removed.
- g. The physical examination should comprise a focused examination, which includes general, respiratory, CV, abdominal, and extremities evaluations.
- h. Vital signs will include body temperature, heart rate, and triplicate blood pressure (systolic and diastolic) measurements. Participants should be in the supine position after at least 10 minutes rest prior to the vital sign measurements.
- i. A single 12-lead ECG will be performed in the supine position after 10 minutes of rest. ECGs are to be assessed for clinical significance by a qualified medical designee at the study site.
- j. For women of childbearing potential only.
- k. FSH test will be performed in women <55 years of age for whom it has been ≥1 year since their last menstrual period.
- 1. At Screening (Visit 1), Visit 4 (Day 84), and EOT, chemistry panel will include HbA1c.

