2.3.4 Safety Endpoints

The safety endpoints include the following:

• Safety and tolerability profile of obicetrapib 10 mg + ezetimibe 10 mg FDC therapy, obicetrapib 10 mg as monotherapy, and ezetimibe 10 mg monotherapy assessed clinical laboratory assessments (chemistry, hematology, and coagulation), vital signs, physical examinations, the incidence of AEs and events of special interest.

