3.1.2 Analysis Visits

Scheduled visits will be assigned to analysis visits as recorded on the CRF.

For each analysis visit, if a scheduled visit occurs within the analysis day window, then the measurement from this scheduled visit will be used. If no scheduled visit occurs or laboratory results of the scheduled visit were unreportable, the unscheduled measurement closest to the target day will be used. If measurements are equidistant to the target day, the later measurement will be used. If laboratory measurements during the scheduled visit were taken while a participant was not in a fasting state and laboratory measurements are available from an unscheduled visit

during which the participant was in a fasting state (and the visit was done within seven days of the scheduled visit), those fasted labs will be utilized in place of the unfasted labs. Otherwise, unscheduled visits will not be re-assigned and will remain labelled as unscheduled.

Early termination (ET) visits will be assigned to analysis visits according to the following visit windows:

Analysis Visit	Target Analysis Day	Low Analysis Day	High Analysis Day
Day 1 (Visit 2)	1	NA	NA
Day 28 (Visit 3)	28	2	56
Day 84 (Visit 4)	84	57	98
Day 112 (Visit 5)	112	99	NA

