Values and changes from baseline will be summarized for CK levels by visit and treatment group and visit. In addition, the number and percent of participants with abnormal CK values will be summarized. These summaries of participants with abnormal CK values will be performed overall, by normal Baseline CK, and by abnormal Baseline CK. Values of CK from Baseline to EOT will be summarized by treatment group and by Baseline eGFR category.

Cases of NODM will be recorded and summarized using the appropriate system organ class. These events will be summarized by severity and relationship to study drug for each treatment group.

Baseline eGFR will be summarized by treatment group for actual value and for baseline eGFR categories. Shift tables of eGFR category from baseline to EOT will be provided by treatment group. Shift tables of urine albumin-creatinine ratio from baseline to EOT will be provided by treatment group.

Participants will be identified as those who have a diagnosis of hypertension in their medical history and received antihypertensive medication(s) at Baseline. If a participant has an adverse event related to hypertension after Baseline (see Appendix B for preferred terms) and has any change in antihypertension medication within 30 days of the start date of the adverse event, that change in antihypertension medication will be considered due to a change in blood pressure. Participants will be identified as those who did not have a prior diagnosis of hypertension in their medical history but had an adverse event of hypertension (see Appendix B) after Baseline. If participants had an adverse event of hypertension and had initiation of antihypertension medication within 30 days of the start date of the adverse event, that initiation of an antihypertension medication will be considered due to a change in blood pressure.

The number and percentage of participants receiving/not receiving antihypertensive medication(s) at Baseline with changes to or initiation of new antihypertensive medication(s) due to changes in blood pressure will be summarized by treatment group.

Cases of macular degeneration will be recorded and summarized using the appropriate system organ class. These events will be summarized by severity and relationship to study drug for each treatment group.

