3.5.3 Clinical Laboratory Tests

Blood samples for clinical laboratory evaluations (chemistry, hematology, and coagulation) will be collected at visits specified in Table 1. Blood samples for chemistry and hematology must be obtained under fasting conditions (ie, after the participant has fasted for a minimum of 8 hours) and before study drug administration. For the purposes of this study, fasting will be defined as nothing by mouth except water and any essential medications. See Appendix B of the protocol for a complete list of analytes.

Laboratory values will be summarized descriptively, including the change from baseline. In addition, shift tables for select parameters will be presented to describe the change in laboratory parameter values at post-baseline visits using normal range categories (low, normal, and high).

Chemistry and hematology laboratory parameters will be listed.

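### SAP 3.5.2 defines renal events of special interest but plans no count of participants who meet them; its eGFR and UACR shift tables run to a single, undefined EOT time point

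*SAP*

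**What the plan says.** SAP 2.3.4 includes in the safety endpoint "the incidence of AEs and events of special interest". SAP 3.5.2 gives the renal ESI three criteria: a fall in eGFR of more than 25% from baseline, an eGFR below 30, or a rise in serum creatinine of at least 0.3 mg/dL. Protocol 8.1.4 and 8.1.4.4 give the same criteria except that the absolute eGFR limit is 15.

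Apart from summaries of baseline eGFR, the renal outputs in SAP 3.5.2 are: "Shift tables of eGFR category from baseline to EOT will be provided by treatment group" and "Shift tables of urine albumin-creatinine ratio from baseline to EOT will be provided by treatment group". The eGFR categories are not stated, and EOT is not defined for these tables.

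Elsewhere, SAP 3.5.3 says: "Laboratory values will be summarized descriptively, including the change from baseline". It adds that "shift tables for select parameters will be presented to describe the change in laboratory parameter values at post-baseline visits", using low, normal and high, and that chemistry is listed. The chemistry panel in Protocol Appendix B contains creatinine and eGFR.

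On visits, footnote c of the Schedule of Procedures gives an EOT Visit at Day 28 to those who stop drug by then, and an EOT Visit to those who withdraw from the study. It then says: "Participants who discontinue study drug between Visit 3 (Day 28) and Visit 4 (Day 84) will not undergo an EOT Visit". On management, Protocol 8.1.4.4 says that, where no other cause is found, "the study drug should be discontinued if participants experience an unexplained, confirmed increase in serum creatinine of" at least 0.3 mg/dL, or a comparable eGFR fall.

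**The concern.** The ESI section sets thresholds and then does not tabulate against them. For ALT, AST, bilirubin and CK the same section plans the number and percentage with abnormal values, and for antihypertensive changes the number and percentage of participants. For renal events it plans neither.

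The shift tables do not fill the gap. They use categories instead of the ESI criteria, creatinine is not in them, and they compare baseline with one later point that many participants do not have if EOT means the EOT Visit. What is at stake is whether a reader of the study report can see, by arm, how many participants met each renal criterion. The protocol intends ESIs to be tracked whether or not they were reported as adverse events (8.1.4), so adverse event tables alone cannot supply that incidence.

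**Working it through.** The plan states no figure for this point, so there is none to reproduce. The check sets the visit plan against the outputs, then tests what a category shift can show.

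**1. Who has an EOT value?** Inputs: Schedule of Procedures, footnote c; Protocol 4.5; SAP 3.5.5.

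| Participant | EOT Visit, read literally | Read as Visit 4/EOT |
|---|---|---|
| Completes treatment | None | Day 84, on drug (blood drawn before that day's dose, Protocol 5.5.3) |
| Stops by Day 28 | Day 28 | Day 28 or Day 84; not stated which |
| Stops between Day 28 and Day 84, stays in study | None | Day 84, off drug |
| Withdraws from study | EOT Visit | EOT Visit |

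The combined Visit 4/EOT label appears in SAP 3.5.5 for physical examinations only. It is the likelier intention, but the shift tables do not say so.

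**2. A decline found at Day 28.** Protocol 8.1.4.4 asks for a repeat, preferably 3 to 7 days after the result is available. If the result were available on Day 28 (an assumption; any delay moves this later), confirmation falls on Day 31 to Day 35. A participant who then stops drug has the next scheduled chemistry on Day 84:
- stop on Day 35: 84 − 35 = 49 days off drug;
- stop on Day 29, before confirmation: 84 − 29 = 55 days off drug.

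If eGFR has recovered by then, the baseline-to-EOT table shows no shift. The repeat is normally unscheduled. Under SAP 3.1.2, apart from replacing missing, unreportable or non-fasting scheduled results, "unscheduled visits will not be re-assigned and will remain labelled as unscheduled". A decline first seen at Day 112 is outside the table too.

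**3. Can a category shift stand in for a fall above 25%?** The bands are an assumption, since the SAP gives none. The largest fall that stays inside a band from L to U is 1 − L/U:
- 60–89: 1 − 60/89 = 32.6%
- 45–59: 1 − 45/59 = 23.7%
- 30–44: 1 − 30/44 = 31.8%
- 15–29: 1 − 15/29 = 48.3%
- a single 30–59 band: 1 − 30/59 = 49.2%

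So every band listed except 45–59 can hide a qualifying fall. From 88 to 64 is (88 − 64)/88 = 27.3% with no shift. Conversely, 61 to 59 is (61 − 59)/61 = 3.3% and does shift.

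**4. How often?** Simulation, with baseline eGFR assumed normal, mean 82, SD 18, truncated to 15–130, and no recovery. The share of falls that cross no band is:

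| Cut points | Falls of 25–30% | Falls of 25–40% |
|---|---|---|
| 15/30/45/60/90 | 17% | 7% |
| 15/30/60/90 | 26% | 16% |

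**5. Do other outputs apply the thresholds?** SAP 3.5.3 gives summaries of change, normal-range shifts for selected parameters, and listings. SAP 3.5.1 gives adverse events by system organ class and preferred term. None uses the 25%, absolute-limit or 0.3 mg/dL criteria.

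**The case against.** A reader might infer that the eGFR shift is the trial's only post-baseline view of renal function. The documents do not support that. There is the UACR shift, and SAP 3.5.3 covers a panel with creatinine and eGFR drawn on Days 28, 84 and 112. A decline at a scheduled Day 28 visit therefore enters the laboratory summaries while the participant is still on drug.

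A reader might also infer that EOT always falls after drug has been stopped in participants with renal decline, and that this is why the events go uncounted. That does not hold either. Stopping is tied to unexplained, confirmed change with no other cause, so others may still be dosing at Day 84, when the sample is on drug. The events go uncounted because no threshold count is specified, wherever EOT falls.

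The cases that do lead to stopping also have another route into the report. Protocol 8.1 makes a laboratory abnormality an adverse event when action with study drug is required, and SAP 3.5.1 tabulates events leading to discontinuation. SAP 3.5 also promises that all safety endpoints will be summarized by arm, so a count might be produced anyway. Finally, the ALT, AST, bilirubin and CK counts are of abnormal values, not explicitly of the ESI limits, so the contrast with those ESIs is one of degree.

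All of this stands, and it narrows the point. It leaves no output in the SAP that gives the incidence of the renal criteria by arm.

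**Conclusion.** The concern holds as a gap in the planned outputs. SAP 3.5.2 specifies no number and percentage for any renal ESI criterion, and the two shift tables it does plan cannot replace one. Their end point is undefined, they can miss a Day 28 decline that later recovered, and they miss some falls above 25%.

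The size depends on assumptions. The 7% to 26% range rests on assumed bands and an assumed baseline distribution. Under those same assumptions, 74% to 93% of such falls do cross a band if there is no recovery. Recovery by Day 84 is a possibility; the documents give no rate for it. It would be going too far to conclude that a renal signal for obicetrapib or the combination would be understated or hidden: no documented figure shows that, and the laboratory summaries, listings and discontinuation tables would show part of it. This is a worthwhile, inexpensive improvement to the safety reporting and does not affect the efficacy conclusions.

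**What to change.** First reconcile the absolute eGFR limit: below 30 in SAP 3.5.2, below 15 in Protocol 8.1.4 and 8.1.4.4. SAP section 5 does not list this as a change from the protocol. It affects any count, because inclusion criterion 7 admits participants with eGFR from 15, so someone entering between 15 and 29 meets the SAP limit at baseline with no decline. Which limit applies is for the sponsor to settle.

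Then, in SAP 3.5.2:
- add the number and percentage of participants, by treatment group, meeting each renal ESI criterion at any post-baseline measurement, including unscheduled and confirmatory values;
- base the eGFR and UACR shift tables on the worst on-treatment value, and show Day 84 and Day 112 separately so that recovery can be seen;
- define EOT and the eGFR categories.

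The CK outputs can stay as planned, since CK already has values by visit and counts of abnormal values.

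The cost is SAP wording and a few more tables from laboratory data already being collected. Worst-value summaries carry more random variation than values at a fixed visit, but this is expected to be similar in all arms.

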3.5.3 Clinical Laboratory Tests

Blood samples for clinical laboratory evaluations (chemistry, hematology, and coagulation) will be collected at visits specified in Table 1. Blood samples for chemistry and hematology must be obtained under fasting conditions (ie, after the participant has fasted for a minimum of 8 hours) and before study drug administration. For the purposes of this study, fasting will be defined as nothing by mouth except water and any essential medications. See Appendix B of the protocol for a complete list of analytes.

Laboratory values will be summarized descriptively, including the change from baseline. In addition, shift tables for select parameters will be presented to describe the change in laboratory parameter values at post-baseline visits using normal range categories (low, normal, and high).

Chemistry and hematology laboratory parameters will be listed.

3.5.4 Vital Signs

Vital signs (body temperature, heart rate and triplicate blood pressure) will be measured at applicable visits as indicated in Table 1. Values will be summarized with descriptive statistics, including the change from baseline at each visit by treatment group and overall.

Vital signs will be listed.

3.5.5 Physical Examinations

Physical examinations (with focused examination on general, respiratory, CV, abdominal, and extremities evaluations) and recording of weight and height will be performed at Screening Visit and Visit 4/EOT. Height will be measured at Screening Visit only and used to calculate body mass index. BMI will be calculated as weight/(height/100)² (kg/m²); rounded and displayed to 1 decimal place.

Physical examination parameters will be recorded as normal, abnormal or not done. Abnormal values will be assessed as clinically significant or not clinically significant. Count and percentages for physical parameters will be summarized by treatment group and in total.

4 ANALYSIS TIMING

4.1 Interim Analysis

No interim analysis is planned.

4.2 Pre-Final Analysis

After the database is locked and exclusions from analysis populations have been finalized, the randomized treatment assignments will be unblinded and the pre-final analysis will be generated. Pre-final tables, figures, and listings (TFLs) will be provided approximately 3 weeks after database lock.

4.3 Final Analysis

After all comments on the pre-final analysis have been resolved and the study database is declared final, the final analysis will be generated. If there were no changes to the pre-final analysis or the study database, the pre-final TFLs may be considered final. In addition to TFLs, SDTM data and ADaM data along with associated files will be provided. Associated files may include annotated case report forms (CRFs), SDTM specifications, SDTM programs, ADaM specifications, ADaM programs, TFL programs, and CDISC Define packages for both SDTM and ADaM data.

5 CHANGES FROM PROTOCOL-SPECIFIED STATISTICAL ANALYSES

There has been one change from the protocol v3.0:

• The inclusion of subgroup analysis.

6 PROGRAMMING SPECIFICATIONS

Analyses will be performed using SAS® version 9.4 or higher. All available data will be presented in subject data listings which will be sorted by subject and visit date as applicable. Detailed Programming Specifications will be provided in a separate document.

APPENDIX B: PREFFERED TERMS FOR HYPERTENSION

Preferred Term
Accelerated hypertension
Blood pressure ambulatory increased
Blood pressure diastolic increased
Blood pressure inadequately controlled
Blood pressure increased
Blood pressure orthostatic increased
Blood pressure systolic increased
Diastolic hypertension
Essential hypertension
Hypertension
Malignant hypertension
Mean arterial pressure increased
Systolic hypertension
Blood pressure abnormal
Blood pressure ambulatory abnormal
Blood pressure diastolic abnormal
Blood pressure orthostatic abnormal
Blood pressure systolic abnormal
Labile blood pressure
Hypertensive crisis
Hypertensive emergency
Hypertensive urgency
Orthostatic hypertension
